8.3. Missing Data

The data after the receipt of rescue therapy will be handled before imputation as below:

Use of rescue therapy: Except OC, all efficacy data on or after the receipt of rescue therapy will be considered as 'not evaluable data' for analysis. For analysis purpose it will be replaced by the worst possible score for endpoint, and considered as 'treatment failure'. However, in OC analysis, all observed data even after the receipt of rescue treatment will be included for analysis, i.e. no imputation for missing data.

In case of diary data, if the date of rescue therapy use is within the analysis visit window, the subject at the analysis visit will be treated as treatment failure except for OC analysis, and the weekly average will be imputed using the worst case value.

Further details for the data handling for rescue therapy are in section 7.

The primary method to impute the missing values will be as follows:

Continuous Endpoints: For continuous endpoints during Initial Period, the MI under MAR assumption approach and the MMRM approach will be used to handle the missing data for the selected secondary endpoints.

CCI

Binary Endpoints: All missing values will be treated as a non-responder for the binary endpoints for primary, key secondary and secondary endpoints during Initial Period. To assess the robustness of non-responder analysis for primary and key secondary endpoints, a tipping point analysis will be performed. The MI under MAR assumption, LOCF, and OC will be used as sensitivity analysis to impute the missing values for the primary and key secondary endpoints.

Adverse events and concomitant medications/procedures: Missing assessment times will have imputed times for the purposes of assessing treatment emergence for AEs or classifying medications/procedures into prior/concomitant. However, the assessment times (start date, stop date, and time if collected from CRF) without imputation will be presented in the listings.

For the start of a concomitant medication/procedure or AE:

- Only the year is reported: If the subject received the first study drug dose in the year reported, then the date of the first dose of study drug will be used as the start date; otherwise, January 1 of the year reported will be used as the start date.

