- The month and year are reported: If the subject received the first study drug in the month and year reported, then the date of the first dose of study drug will be used as the start date; otherwise, the first day of the month and year will be used as the start date.

This document is confidential.

- The time is collected but missing: If the start date is the same as the date the subject started receiving study drug, then the time of the first dose of study drug will be used as the start time; otherwise, 00:00 will be used as the start time.

For the end of a concomitant medication/procedure or AE:

- Only the year is reported: The earlier between December 31 of the year reported and the date of the last study contact with the subject will be used as the stop date.
- The month and year are reported: The earlier between the last date of the month and year reported and the date of the final contact with the subject will be used as the stop date.
- The time is collected but missing: 23:59 (or 23:59:59 if collected up to seconds) will be used as the stop time.

If an AE has the start date completely missing and the stop date on/after the first dose date of study drug, this AE will be considered as treatment emergent (TEAE).

If a medication/procedure has the stop date completely missing, this medication/procedure will be considered as ongoing and concomitant. If the start date of a medication/procedure is completely missing and impossible to identify different by stop date, this medication will be considered as concomitant.

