9.5. Medication

Medications will be classified and summarized on the ITT population as follows:

- Prior medications are defined as those which stop before the first injection of study drug during the study.
 - Prior medication before informed consent signed is defined as those stopped before the date of informed consent signed to the study.
 - Prior medication during screening period is defined as those stopped during screening period (on or after the informed consent date until before the first treatment date).
- Concomitant medications are defined as those started or stopped on or after the first injection of study drug.

This document is confidential.

- Medication during treatment period are defined as those started, stopped, or ongoing during the period.
 - Medication during Initial Period is defined if started or ongoing or ended during Initial Period.
 - Medication during Maintenance Period is defined if started or ongoing or ended during Maintenance period.
 - If early discontinued during Initial (or Maintenance) Period, the treatment period will be defined from start of treatment till 4 weeks after the last treatment or early discontinuation date whichever is earlier.
- Medication during follow-up period are defined as those started, stopped, or ongoing during the period.
 - Follow-up Period is defined from post treatment period to follow-up visit date.
 - Medication during Follow-up Period will be summarized in accordance with the respective period (Initial or Maintenance).
- If medication is being used continuously during both periods (e.g., started in the Initial period and ended or ongoing in the Maintenance period), it will be counted for each period.

If the stop date and 'ongoing' are missing then the medication will be considered as concomitant medication. If stop date is partially missing, the medication will be considered as concomitant unless the non-missing part of date proves it ended prior to the first treatment date.

Medications (prior, concomitant and rescue medications) will be coded using Version B3 March 2022 of the World Health Organization's Drug Dictionary (WHO DD). Preferred Anatomical Therapeutic Chemical (ATC) coding will be performed.

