13.1. Adverse Events

Adverse events (AEs) will be coded using MedDRA Version 25.0, March 2022.

Treatment-emergent AEs, defined as those AEs occurring after the first administration of study treatment until end of study, will be tabulated in frequency tables by System Organ Class (SOC) and Preferred Term (PT) based on the Medical Dictionary for Regulatory Activities for each study period (Initial Period, Maintenance Period, and Follow-up Period). Missing date information will be handled using the algorithm described in Section 8.3.

Additional summary tables by SOC and PT will be provided for SAEs, AEs related to the study drug(s), AEs related to the study procedure, adverse events of special interest (AESIs), and AEs leading to treatment discontinuation and study withdrawal.

AEs will be summarized using the number and percent of subjects reporting each SOC and PT and sorted alphabetically by SOC and by descending frequency of PT within SOC.

Subjects who experienced multiple events within the same SOC will be counted once in the SOC summary. When summarizing by causality or maximum severity, if a subject experiences more than 1 occurrence of the same AE, the occurrence with the greatest severity and the closest association with the study drug will be used in summary tables. For summary by maximum severity, subjects who experience multiple occurrence of an AE, the most severe category for each SOC and for each PT within each SOC will be considered in the summary.

TEAEs related to study drug/study procedure are those that are identified as reasonable possibility.

If relationship or severity is missing, the event will be considered as AE related to study drug/study procedure or severe AE.

An AESI is a noteworthy treatment-emergent event for the study drug that should be monitored closely and reported promptly. An AESI can be either serious or non-serious. Based on the potential risks of nemolizumab and the risks associated with biologics in general (i.e., class effects), the following AEs will be considered as AESIs: Injection-related reactions, Newly diagnosed asthma or worsening of asthma, Infections, Peripheral edema:limbs, bilateral, Facial edema and elevated ALT or AST (>3xULN) in combination with elevated Bilirubin (>2xULN).

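### The SAP's partial-date rule for adverse events ignores a known stop date, so an event that resolved before the first dose can be counted as treatment-emergent

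*SAP*

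**What the plan says.** SAP Section 8.3 imputes incomplete AE and medication dates "for the purposes of assessing treatment emergence for AEs or classifying medications/procedures into prior/concomitant". For start dates:

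- Year only: "If the subject received the first study drug dose in the year reported, then the date of the first dose of study drug" becomes the start; otherwise 1 January of that year.
- Month and year: "If the subject received the first study drug in the month and year reported, then the date of the first dose of study drug" becomes the start; "otherwise, the first day of the month and year will be used as the start date".
- Start completely missing: the stop date decides. The condition for treatment emergence is "If an AE has the start date completely missing and the stop date on/after the first dose date of study drug".

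SAP Section 13.1 defines a treatment-emergent AE (TEAE) by occurrence after the first administration of study treatment. It tabulates TEAEs by Initial, Maintenance and Follow-up Period, and adds: "Missing date information will be handled using the algorithm described in Section 8.3".

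For medications, SAP Section 9.5 defines prior use by a stop before the first injection. It also states: "Concomitant medications are defined as those started or stopped on or after the first injection of study drug". Section 9.4 is similar for procedures. Both sections test a partial stop date against the first treatment date.

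Protocol Section 9.2.1 collects AEs from consent, so events before the first dose are in the database.

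**The concern.** Moving an uncertain onset to the first dose is a sensible default when the record leaves open whether the event began before or after dosing. A known stop before the first dose closes that question. The rule nevertheless overrides it and produces a record whose onset follows its own resolution. A resolved screening event then enters the TEAE tables of whichever arm the subject was assigned to.

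Two lesser consequences come from the same rule. An imputed start can make a medication or procedure that had already stopped also meet the concomitant definition, although its stop date makes it prior. And because no default refers to the Week 16 dose, an event that began under the re-randomised regimen (Q4W, Q8W or placebo) can be counted in the Initial Period, under the initial regimen.

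**Working it through.** The plan states no figure for this point, so there is none to reproduce. The check applies the Section 8.3 rules to dates. All calendar dates below are illustrations.

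**1. Known stop before first dose.** Start June 2021, stop 10 June 2021, first dose 22 June 2021. Month and year match the first dose, so the imputed start is 22 June, and 22 − 10 = 12 days after the stop. A start recorded only as 2021 gives the same result. The event becomes a TEAE, taking an imputed onset on the first-dose date as treatment-emergent, which is the evident purpose of the rule.

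If the same event had no start date at all, the completely-missing rule would not make it a TEAE, because its stop precedes dosing. The record with more information gets the worse classification.

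**2. How often the first-dose branch applies to a partly dated screening event.** Assumptions: first dose uniform over a 365-day year; onset uniform over the 28 days before it. Combinations: 365 × 28 = 10,220.

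- Year only: onset falls in the previous year in 28 + 27 + … + 1 = 406 combinations. Share set to first dose = 1 − 406/10,220 = 96.0%.
- Month and year: onset falls in an earlier month in 12 × 406 = 4,872 combinations. Share = 1 − 4,872/10,220 = 52.3%.

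These shares hold whatever the stop date, because the rule never reads it.

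**3. Medications.** Ciclosporin, start recorded as 2021, stop 10 February 2021, first dose 15 April 2021. The stop makes it prior under Section 9.5. The imputed start of 15 April also meets the started-on-or-after wording. The two definitions overlap, and no sentence says which prevails.

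**4. Period assignment.** Week 16 is 112 days after the first dose (target Day 113 in SAP Section 8.4).

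| First dose | Week 16 | True onset | Recorded as | Imputed start | Period assigned |
|---|---|---|---|---|---|
| 20 Mar 2021 | 10 Jul 2021 | 5 Oct 2021 | 2021 | 20 Mar 2021 | Initial |
| 20 Mar 2021 | 10 Jul 2021 | 5 Oct 2021 | Oct 2021 | 1 Oct 2021 | Maintenance |
| 20 Mar 2021 | 10 Jul 2021 | 25 Jul 2021 | Jul 2021 | 1 Jul 2021 | Initial |
| 1 Nov 2021 | 21 Feb 2022 | 10 May 2022 | 2022 | 1 Jan 2022 | Initial |

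With onset uniform over Days 113 to 337 (225 days) and first dose uniform over a year, there are 365 × 225 = 82,125 combinations.

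- Year only, onset in the first-dose year: first doses on the first 29 days of the year contribute 29 × 225 = 6,525, and later ones 224 + 223 + … + 1 = 25,200. Total 31,725, or 38.6%, set to the first dose.
- Year only, onset in the next year with 1 January before Week 16: 111 first-dose dates × 225 = 24,975, or 30.4%.
- Together 69.0% move to the Initial Period, and 31.0% stay in Maintenance.
- Month and year: only onsets in the calendar month of Week 16 can move. A month of L days contributes L(L − 1)/2. This gives 7 × 465 + 4 × 435 + 378 = 5,373, or 6.5%.
- Month and year through the first-dose branch: none. Week 16 is at least 112 − 5 = 107 days after first dose, even at the early edge of the visit window.

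**5. Scale of one misplaced event.** Protocol Section 8.1 expects about 190 re-randomised nemolizumab subjects, so 190/3 ≈ 63 per arm. If the only such event of one subject leaves a maintenance arm, that arm's incidence changes by 1/63 ≈ 1.6 percentage points.

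**The case against.** The strongest reply has four parts.

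- **The default is conservative and the same in both blinded arms.** This stands where timing is uncertain. It does not answer the case where the stop date settles the timing. Sections 9.4 and 9.5 accept that principle: a partial stop date leads to concomitant status unless its known part proves the treatment ended earlier.
- **Partial AE dates should be rare.** The protocol requires onset and resolution dates and asks about AEs at every visit, so a year-only AE late in the study is unlikely. Listings show unimputed dates, so affected records can be traced. This stands and limits the size of the problem. The tables would still carry onset-after-stop records.
- **Drugs are already handled.** A reader might infer that washed-out systemic therapies become concomitant. The documents do not support that: prior status is set by the stop date. What remains is the overlap in step 3.
- **Section 8.3 does not name period assignment as a purpose.** True; the link comes from Section 13.1. A reader might also infer that the first-dose branch moves maintenance events recorded by month and year. It cannot (step 4); those move only through the first-of-month default. TEAE tables for the overall study period do not depend on the split between periods.

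**Conclusion.** The point holds for AEs. As written, Section 8.3 gives a wrong result, not merely an incomplete one, when a partly dated AE has a known stop before the first dose and the reported part of its start matches that dose. The overlap for medications and procedures and the missing Week 16 anchor are secondary.

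The percentages are shares of partly dated records under uniform dates. They do not estimate how many table entries would change, because the documents do not give the number of such records. A reader might infer that the safety comparison is materially distorted; nothing in the documents shows that. Efficacy, alpha and power are unaffected. This is a minor correction, worth making because it is cheap and removes impossible records from the tables.

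**What to change.** In SAP Section 8.3, apply the first-dose imputation to a partial AE start only if the stop date is missing or on or after the first dose. If the stop date, or its known part, proves that the AE ended before the first dose, classify the AE as pre-treatment.

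In Sections 9.4 and 9.5, add that a medication or procedure whose stop precedes first treatment is prior only, whatever start date is imputed.

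State a period-assignment rule for Section 13.1 using dates already collected. For example, if a partial start spans the Week 16 dose in a subject continuing into Maintenance, and the stop date does not rule it out, use the Week 16 dose date. Repeat the by-period summary with the alternative assignment, since this rule can move a true Week 15 event into Maintenance. The rule should not depend on when an AE was first reported: the AE data listed in protocol Section 9.2.1 include no such date.

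The cost is about three sentences, a short programming change and one repeated by-period summary. No new data are needed.

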8.4. Analysis Visit Windows

Efficacy by-visit summaries will use the analysis visit. Unscheduled and early termination visits will be windowed based on the following analysis visit window which is based on study day. If multiple measurements are taken within the same window, the one taken closest to the target study day will be used for the analysis. If there are multiple measurements with same difference from target day, the later assessment should be used for the analysis.

Table 8-1: Analysis Visit Window

Analysis Visit	Target Study Day	Visit Window for EASI, IGA, CCI
Baseline	1	<=1
Week 4	29	2 to 42
Week 8	57	43 to 70
Week 12	85	71 to 98
Week 15	106	NA
Week 16	113	99 to 126
Week 20	141	127 to 154
Week 24	169	155 to 182
Week 28	197	183 to 210
Week 32	225	211 to 238
Week 36	253	239 to 266
Week 40	281	267 to 294
Week 44	309	295 to 322

This document is confidential.

Week 48	337	>=323	CCI
---------	-----	-------	-----

CCI Visit window after Week 16 will not be applicable for PIQs.

CCI

For the diary data at post-baseline visit, only the diary data assessed within the timeframe below (+1 hour to end time in spec) will be considered for analysis. If >1 diary recorded on a day (within window), only one of them to take for analysis (i.e. latest one for evening diary, earliest one for morning diary).

- Evening assessment (PP/CCI NRS, CCI recorded from 17:00:00 to 00:59:59 CCI

Consecutive daily assessment:

For the evening assessments (PP NRS, CCI) during Initial Period, the daily data collected up to Week 16 will be classified into analysis visits considering the data during the 7 days immediately preceding the target study day of analysis visit. Similarly, for the morning assessment (CCI) during Initial Period, the 7 days data up to the target study day will be classified into analysis visit. Details of the analysis visit window are in the table below. Only the data belongs to Initial Period will be considered for classifying the analysis visit in Initial Period.

Table 8-2: Analysis Visit Window for Evening and Morning Assessments during Initial Period

Analysis Visit	Target Study Day of Analysis Visit	Visit Window for evening assessment (PP NRS, CCI)	CCI
Baseline*	1	-7 to -1	
Week 1	8	1 to 7	
Week 2	15	8 to 14	
Week 3	22	15 to 21	
Week 4	29	22 to 28	
Week 5	36	29 to 35	
Week 6	43	36 to 42	
Week 7	50	43 to 49	
Week 8	57	50 to 56	
Week 9	64	57 to 63	
Week 10	71	64 to 70	
Week 11	78	71 to 77	
Week 12	85	78 to 84	
Week 13	92	85 to 91	
Week 14	99	92 to 98	
Week 15	106	99 to 105	
Week 16**	113	106 to 112 before dosing	

* if there are less than 4 days non-missing data available within window, the lower bound of interval will be extended up to 7 additional days to obtain 4 days non-missing data for Baseline weekly score calculation. The timeframe window will not be considered.

** if <4 days non-missing data within Week 16 window, the upper bound will be extended first up to +5 days to obtain 4 non-missing data. If still <4 non-missing data after extending the upper bound, the lower bound will be extended again up to +5 days to obtain 4 days non-missing data. For evening assessment, only the data before Week 16 dosing (or re-randomization if missing Week 16 dosing) will be considered for Initial Treatment Period analysis.

This document is confidential.

1.0

CD14152.SPR118169.SAP.V01

CCI [Redacted]

CCI [Redacted] The same window with evening assessment (PP NRS, CCI [Redacted] in Table 8-2 will be used for Initial Period. For Maintenance Period, the target study day of Week 20, Week 24, Week 28, Week 32, Week 36, Week 40, Week 44 and Week 48 will be Day 141, Day 169, Day 197, Day 225, Day 253, Day 281, Day 309, and Day 337. If the data reported within analysis visit window but after week 16 dosing, it won't be part of initial period. The extended timeframe (+1 hour to end time) to be considered.

Intermittent daily assessment before the visit:

For the evening assessments (PP NRS and CCI [Redacted] the 7 days immediately preceding the actual subject visit date will be classified into the analysis visit. i.e., from 'actual subject visit date - 7 days' to 'actual subject visit date - 1 day'. Similarly, for the morning assessments (CCI [Redacted] the 7 days data from 'actual subject visit date - 6 days' to 'actual subject visit date' will be classified into the analysis visit. In maintenance period, the diary data will not be collected daily, so consider dosing date/time and include data for calculation only if it's done within analysis visit window/timeframe and before dosing.

In case of missing/skipped visit, unscheduled or early termination visit, the diary data will be windowed based on the study day (see Tables 8-3 and 8-4). If a subject missed/skipped a visit due to any reason (e.g., skipped a visit due to COVID-19), the diary data which have been reported during that time will be mapped to the analysis visit based on the study day and 7 days consecutive data will be classified into the analysis visit as in the tables below. For the unscheduled or early termination visit data, the same approach will be applied to window the data into analysis visit.

CCI [Redacted]

Table 8-3: Analysis Visit Window for Missing/Skipped Visit, Unscheduled or Early termination Visit for PP/CCI [Redacted] NRS and CCI [Redacted]

Analysis Visit	Target Study Day of Analysis Visit	Visit Window for evening assessment (PP NRS, CCI [Redacted])*
Week 24	169	162 to 168
Week 32	225	218 to 224
Week 40	281	274 to 280
Week 48	337	330 to 336

CCI [Redacted]

* for evening diary, only the data before dosing on the clinic visit date will be considered for analysis.

CCI [Redacted]

Approved 10-Nov-2022 00:00:00

This document is confidential.

* if <4 days non-missing data within Week 16 window, the upper bound will be extended first up to +5 days to obtain 4 non-missing data. If still <4 non-missing data after extending the upper bound, the lower bound will be extended again up to +5 days to obtain 4 days non-missing data. Only the data before Week 16 dosing (or re-randomization if missing Week 16 dosing) will be considered for Initial Treatment Period analysis.

For efficacy, where two or more assessments (including both scheduled and unscheduled assessments) are available for the same visit interval, the one closest to the target visit date will be used for the summary and analyses. Safety and CCI data will not be windowed for by-visit summary. i.e., scheduled visit data will be used for analysis.

